**Sample size and accrual:** This two arm randomized study will determine if there are differences in the change in PSA slope (post supplementation minus pre supplementation) between patients supplementing with MPX (Arm A) and patients that are not (Arm B). The accrual rate for each site is expected to be 1 patient per month. With 16 to 17 sites, is expected that we could accrue 500 patients over 4 years, for which we will have baseline MnSOD genotype and baseline antioxidant status, of which approximately 80 would be of the required AA genotype and eligible for randomization to MPX or placebo. Overall the study would take 4 years of accrual and another year for follow-up. PSA slope will be defined by the linear regression line of the natural log of PSA (in ng/mL) against time (in months). The primary statistical analysis will be an analysis of covariance (ANCOVA) to compare the two arms at the final analysis, adjusting for baseline PSA slope. Implications of the sample size are given based on simulations which include a single interim analysis for futility midway through the trial. The predictive probability approach for the futility analysis is described in the interim analysis section below. Based on the previous study of MPX at Hopkins, we conservatively estimate that the difference in the post-treatment PSA slope (MPX minus placebo), adjusting for pre-treatment PSA, in this group of patients with the AA genotype will be -0.05 with the MPX arm having lower post-treatment slopes (MPX slope 0.033 ng/mL/month versus untreated 0.083 ng/mL/month). Patients with the AA genotype will be randomized to MPX (Arm A) and placebo (Arm B) in a 1:1 ratio. Using a two sided 5% type I error allowance, a sample size of 78 (39 per arm), and minimal correlation between the pre and post treatment PSA slopes, this study will have 83% power to detect a difference in post-study PSA slope of -0.05. Use of the ANCOVA design with covariate adjustment for pre-treatment PSA slope will tend to increase the power depending on the level of the correlation between paired PSA slope measurements (i.e., pre- and post-treatment). As an example, for a correlation ( $\rho$ ) of 0.30, the power would increase to 87%.

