6. Calculate the predicted probability of rejecting the null hypothesis at the end of the study.

If interim analysis simulations indicate that the probability of a successful trial would be less than 10%, we will consider stopping the trial for futility. The table below gives the operating characteristics of the monitoring plan based on 2000 simulations for different scenarios, each scenario corresponding to different treatment effects and different levels of correlation between the pre-treatment and post-treatment PSA slope. The seventh row shows results using the hypothesized treatment effect of a mean difference of -0.05 with a standard deviation of 0.075, and minimal correlation. We do expect some correlation between pre and post-treatment values, so power will tend to increase with increasing correlation. The significance level for the final analysis is 0.05. Scenarios 1-3 give operating characteristics under the null (no treatment effect).

**Table 1.** Operating characteristics of monitoring rule from 2000 simulated studies with one interim analysis based on 100 predicted study conclusions and final analysis based on an ANCOVA model. Simulations use a *g*-prior with  $g=39$  (i.e. the sample size at the time of the interim analysis). All simulations assume the standard deviation of post-treatment PSA slope is 0.075.

Scenario	Treatment Effect	Correlation (pre- and post-treatment measures)	Stop for Futility %	Would have stopped for Futility and would have Rejected %	Overall studies rejecting Ho %
1	0.0	0.1	34.0%	0.10%	4.3%
2	0.0	0.2	33.5%	0.35%	5.6%
3	0.0	0.3	34.5%	0.20%	4.4%
4	-0.025	0.1	21.9%	1.00%	31.8%
5	-0.025	0.2	20.4%	0.80%	30.6%
6	-0.025	0.3	17.5%	1.40%	35.0%
7	-0.050	0.1	4.5%	1.25%	82.7%
8	-0.050	0.2	4.4%	0.75%	81.9%

9	-0.050	0.3	3.0%	0.95%	87.3%
10	-0.075	0.1	0.4%	0.30%	98.8%
11	-0.075	0.2	0.4%	0.20%	99.1%
12	-0.075	0.3	0.2%	0.15%	99.7%

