## **11.2 Secondary Efficacy Assessment**

**PSA Doubling Time (PSADT):** The PSADT will be calculated as  $\ln(2)$  ( $=0.693$ ) /  $\beta$  ( $=$ slope of the linear regression fit to  $\ln$  PSA vs. time in months). If the patient's slope is less than or equal to zero, we will assign them a PSADT of 100 months, which is consistent with the literature.

A secondary statistical test of the difference between the two groups will be assessed by a nonparametric Wilcoxon Rank Sum test of the percentage change in PSADT (logarithm of the ratio of PSADT on-study divided by the pre-treatment PSADT). We will also analyze the log of the PSADT ratio by the analysis of variance (ANOVA) adjusted for the stratification factors. Confidence intervals (95%) for the change from baseline in PSADT will also be computed for the two dose groups. The paired t-test (or Wilcoxon signed-rank test) will be used to assess the within treatment group differences of PSADT on study compared to the baseline. Patients with negative slopes will be assigned PSADT of 100 months.

**PSA Reduction of  $\geq 50\%$  / Objective Response:** An objective response (OR) is defined as a decrease in PSA by 50% or more after the start of treatment. The objective response rate (ORR) is estimated as the fraction of men for whom an objective response is observed. The time to objective response, defined as the time from start of treatment to an observed objective response, as well as the average duration of response, defined as the time from objective response to disease progression, will also be summarized and compared between groups. To further summarize PSA responses, the percentage change in PSA from baseline at 24 and 48 weeks will be presented in the form of waterfall plots.

**PSA Progression:** The distribution of time to PSA progression will be estimated using Kaplan-Meier method for both treatment groups combined and separately. The stratified logrank test will be used to test the hypothesis that the time to PSA progression distributions for the 2 treatment groups are the same. The same stratification factors used for the randomization will be used to stratify the logrank test.

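### The between-arm PSADT tests in section 11.2 analyse a ratio to baseline instead of adjusting for baseline, which costs power, mainly in the unadjusted Wilcoxon test

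*Combined protocol and SAP*

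**What the plan says.** Section 11.2 (PSA Doubling Time) names two between-arm tests. The first is a "nonparametric Wilcoxon Rank Sum test of the percentage change in PSADT (logarithm of the ratio of PSADT on-study divided by the pre-treatment PSADT"), with no covariates. The second reads: "We will also analyze the log of the PSADT ratio by the analysis of variance (ANOVA) adjusted for the stratification factors". The stratification factors (section 4.1 and section 11, Randomization) are Grade Group and pre-treatment PSADT split at 9 months, so baseline PSADT enters the ANOVA only in two classes. A patient whose on-study slope is zero or negative is given a PSADT of 100 months. No power is stated for either test.

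The primary analysis is built differently. Sections 11 and 11.1 specify an ANCOVA of the on-study log slope with arm and continuous baseline slope as covariates, and section 11 says that this adjustment tends to raise power. The design case assumes "minimal correlation between the pre and post treatment PSA slopes". Table 1 covers correlations of 0.1, 0.2 and 0.3 only.

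**The concern.** The log of a ratio is a difference of logs, so both PSADT tests compare change scores. A change score subtracts the whole baseline value, however weakly baseline predicts the on-study value. When the correlation is low, that subtraction adds more noise than it removes. ANCOVA estimates how much of the baseline to subtract and, in large samples, cannot do worse.

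The plan expects a low correlation and uses ANCOVA for the primary endpoint, but not for the first secondary objective. At stake is a PSADT test that misses an effect which the same data would show under baseline adjustment. If the primary ANCOVA succeeded and the Wilcoxon test did not, the report would seem to contradict itself, partly because baseline was handled in two ways.

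**Working it through.** **Inputs from section 11.** "Using a two sided 5% type I error allowance, a sample size of 78 (39 per arm"); difference 0.05 and SD 0.075 ("hypothesized treatment effect of a mean difference of -0.05 with a standard deviation of 0.075, and minimal correlation"); correlation ρ of 0.1 to 0.3 (Table 1). These are log-slope figures. **Not in the documents:** the SD of pre-treatment slope or of log pre-treatment PSADT, and any correlation on the PSADT scale.

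**Step 1: reproduce the stated power.** The ANCOVA residual SD is 0.075·√(1−ρ²). With 39 per arm and a difference of 0.05, the noncentral t gives 83.2% at ρ = 0.1 and 86.1% at ρ = 0.3 (normal approximation 84.1% and 87.0%). The plan states 83% and 87%, so its figures reproduce.

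**Step 2: the principle.** Let k = SD pre / SD post, and take the on-study variance as 1.

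- Change-score variance: 1 + k² − 2ρk.
- ANCOVA variance: 1 − ρ².
- The difference is (k − ρ)², which is never negative.
- The change score is noisier than the on-study value alone when k > 2ρ, that is k above 0.2 at ρ = 0.1 and above 0.6 at ρ = 0.3.

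Power of an unadjusted t test on a normal change score, against ANCOVA (noncentral t):

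| k | ρ = 0.1 | ρ = 0.3 |
|---|---|---|
| 0.5 | 77% vs 83% | 85% vs 86% |
| 0.75 | 69% vs 83% | 79% vs 86% |
| 1.0 | 58% vs 83% | 69% vs 86% |

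This shows the direction and the dependence on k. It describes neither planned test, because one is rank-based and the other is stratum-adjusted.

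**Step 3: the planned tests on the PSADT scale.** On-study slopes have means 0.083 and 0.033 and SD 0.075; on-study PSADT is capped at 100 months; the stratum cut is 9 months; 39 per arm. Assumed: median pre-treatment PSADT 9 months, and the SD of its log as shown. There were 2,500 trials per cell, so a power near 60% has a standard error of √(0.6·0.4/2500), about 1 point.

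| ρ | SD of log pre-treatment PSADT | Wilcoxon on ratio | Rank ANCOVA | ANOVA of ratio + strata | ANCOVA of log PSADT |
|---|---|---|---|---|---|
| 0.1 | 0.4 | 76% | 80% | 77% | 77% |
| 0.1 | 0.7 | 68% | 79% | 73% | 75% |
| 0.1 | 1.0 | 59% | 79% | 69% | 77% |
| 0.3 | 0.4 | 81% | 82% | 80% | 80% |
| 0.3 | 0.7 | 75% | 81% | 77% | 78% |
| 0.3 | 1.0 | 69% | 83% | 76% | 80% |

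A separate run with SDs of 0.3, 0.5, 0.7 and 1.0 gave Wilcoxon losses against rank ANCOVA of about 2, 5, 11 and 19 points at ρ = 0.1, and 0 to 15 points at ρ = 0.3. The stratum-adjusted ANOVA lost about 0 to 7 points. The two runs agree within simulation error, and the verdict uses the second. At ρ = 0.1 a Wilcoxon test on on-study PSADT alone has about 79% power, so there the ratio does worse than ignoring baseline.

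**Step 4: separate the ratio from the PSADT scale.** A further simulation (4,000 trials) drew pre-treatment slopes with mean 0.077 and SD 0.075, kept them positive, and used ρ = 0.1. Power was 82.8% for slope ANCOVA, 75.6% for log-PSADT ANCOVA, 65.8% for Wilcoxon on the ratio and 71.2% for the stratum-adjusted ANOVA. The gap of 82.8 − 75.6 = 7.2 points comes from the PSADT transformation and the 100-month value. The ratio accounts for 75.6 − 65.8 = 9.8 points (Wilcoxon) and 75.6 − 71.2 = 4.4 points (ANOVA).

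**The case against.** The strongest reply is about size. A reader might infer from Step 2 that both tests lose 20 points or more. The documents do not support that.

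- The ANOVA already adjusts for pre-treatment PSADT in two classes, which recovers much of the loss.
- The equal-SD case (k = 1) is not given anywhere and is hard to square with eligibility. Section 3 requires a positive pre-treatment PSADT, so baseline is truncated while on-study slopes are not. At the planning values, Φ(−0.083/0.075) = 13% of placebo and Φ(−0.033/0.075) = 33% of MPX on-study slopes are zero or below and go to 100 months, which widens the on-study distribution.
- Section 11 expects average doubling times of 6 to 15 months. If that interval is read as ±1 SD of individual values (an assumption, since it is stated for averages), the log SD is ln(15/6)/2 = 0.46. In that region the Wilcoxon loss is about 5 points or less.
- Section 11 expects some correlation, so 0.1 is a cautious case.

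All of this stands as a limit on the size. It does not remove the inefficiency.

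A second reply is about importance. The objective in section 1.2 is worded as estimation, section 11.4 ranks every non-primary test as secondary or lower, and the primary ANCOVA already tests the same slope data with baseline adjustment. This also stands: no trial conclusion should turn on these tests.

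A third reply is that the ratio preserves comparability. Section 5 describes change from baseline in PSADT, and change in PSADT was the phase II endpoint. Reporting the ratio descriptively meets that need. The reply that a parametric ANCOVA would carry the 100-month values is true, but the planned ANOVA carries them too.

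**Conclusion.** The point holds as a modest inefficiency in secondary tests. Both between-arm PSADT tests use a change score where baseline adjustment would be more efficient at the correlations the plan considers.

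The Wilcoxon test carries most of the loss: about 2 to 19 points against rank ANCOVA at ρ = 0.1 and 0 to 15 points at ρ = 0.3. The upper ends need an SD of log pre-treatment PSADT of 1.0. The stratum-adjusted ANOVA loses about 0 to 7 points.

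These figures rest on two assumptions: the range of 0.3 to 1.0 for that SD, and the use of the slope correlation and slope SD to generate the PSADT data. If baseline PSADT varies little, the loss is small. A reader should not infer that the primary result or its stated power is weakened; the primary model already adjusts for continuous baseline slope and its power reproduces.

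**What to change.** In section 11.2:

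- Replace the Wilcoxon test on the ratio with a rank ANCOVA: ranks of on-study PSADT compared between arms, adjusted for ranks of pre-treatment PSADT.
- In the parametric model, use log on-study PSADT as the outcome, with arm, continuous log pre-treatment PSADT and the stratification factors as covariates.
- Keep the ratio of on-study to pre-treatment PSADT, with its confidence interval, as a descriptive summary by arm for comparison with phase II.

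The cost is SAP wording; the data are already collected. The small downside is that the ratio would no longer be the tested quantity.

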### 2.2.3 Phase I and Phase II Clinical Studies of Muscadine Grape Skin Extract

Early clinical studies have now also been completed. A phase I trial was done in 14 men with biochemical recurrent prostate cancer. The phase I study was designed as a dose finding study, showing that the maximal dose, 4,000mg daily, was well tolerated. That dose was chosen as the maximum since it consists of 8 capsules and taking more than that a day raised concerns for adherence to therapy. Six of the 14 patients received the maximum dose. The most common side effect was flatulence (4 of 14 patients reported). Soft stools, abdominal distention and eructation were also reported and all were grade 1 toxicities. There were no grade 4 adverse events and no study drug related grade 3 adverse events. In this early phase trial, 64% of patients had increases in PSADT with 44% of those who had an increase having an increase of more than 6 months.

Given the safety and possible signal of benefit, a phase II trial was completed. This was a randomized, double-blind trial of 112 men with biochemical recurrent prostate cancer who were assigned to receive either placebo, 500mg or 4,000mg of MPX in a 1:2:2 design. The primary endpoint was change in PSADT. There was no significant difference found between the three groups ( $p=0.81$ ) with a change of 0.9 months seen in the placebo group, 1.5 month change in the 500mg group and 0.9 month change seen in the high dose group. There was only one patient in the 4,000mg dose group who had a decrease in PSA of  $\geq 50\%$ . There were no new safety signals noted in this trial.

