## 3. Eligibility Criteria

### 3.1 Inclusion Criteria

Patients meeting the following conditions are eligible for registration and participation in the study:

1. Subject has histologically or cytologically confirmed adenocarcinoma of the prostate
2. Subject has undergone definitive treatment (surgery, surgery with radiation therapy, cryotherapy, radiation therapy or brachytherapy) for the primary prostate tumor (prior chemotherapy is not allowed).

- a. A subject with a rising PSA post-prostatectomy should consider radiation as a potentially curative alternative. If subject declines radiation or is not a candidate for radiation, he may be considered eligible in this setting.
3. Subject has a rising PSA on a minimum of 3 time points (2 rises) within the 12 months prior to study initiation (this will include the PSA measurement taken at the screening visit, but not at the baseline day 0 study visit). The three time points must be at least 21 days apart. Note: Fluctuations in PSA are allowed per Bubley et al 1999 working group criteria. 
4. For purposes of calculating PSADT:
  - a) All PSA values used in the calculation should be  $\geq 0.10$  ng/ml and overall should follow a rising trend;
  - b) Record every available PSA drawn within the last 12 months;
  - c) The minimum requirement is 3 PSA values;
  - d) For radiotherapy only patients, record PSA nadir value and collection date.PSADT must be positive according to Memorial Sloan Kettering Cancer Center Prostate Cancer Nomograms under this link:  
<http://www.mskcc.org/applications/nomograms/prostate/PsaDoublingTime.aspx>
5. At least 2 PSA rises need to be after a normal Testosterone for those patients who had prior hormone therapy.
6. One of the following criteria must be met.
  - a. Absolute level of PSA  $>0.2$ ng/mL following surgery. (surgery only)
  - b. Absolute level of PSA  $>0.2$ ng/mL for subjects treated with multiple treatment modalities (e.g., surgery + radiation, surgery + cryotherapy, etc.).
  - c. A rise by 2 ng/mL or more above the nadir PSA will be considered the standard definition for biochemical failure after radiation therapy with or without hormonal therapy. (radiation only)
7. Subject is  $>18$  years of age.
8. Subject has life expectancy of greater than 12 months.
9. Subject has ECOG performance status 0, 1 or 2
10. Subject has testosterone level of  $\geq 150$  ng/dL at screening.
11. Subject has normal organ and marrow function as defined below:

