### **3.2 Exclusion Criteria**

Subjects meeting the following conditions are not eligible for participation in the study:

1. Subject has known radiographic evidence of metastatic disease, except for presence of positive lymph nodes from the surgical pathology. Pelvic/intraperitoneal lymph nodes less than 1.5 cm maybe considered nonspecific and the patient would be eligible (including those patients who were treated with radiation for oligometastatic disease). If there is any clinical suspicion for metastatic disease, CT and Bone Scan must be performed to rule out metastatic disease, within the last three months, per standard of care.
2. Subject has received any therapies that modulate testosterone levels (e.g., androgen ablative/anti-androgen therapy, 5 alpha reductase inhibitors) for a minimum of 12 months prior to study.
3. Subject has had prior or concomitant treatment with experimental drugs, high dose steroids, or any other cancer treatment within 4 weeks prior to the first dose of the study product.
4. Subject has consumed any Muscadine Plus over the past 2 months.
5. Subject has a known allergy to muscadine grapes, ellagic acid or rice.
6. Subject has uncontrolled concurrent illness including, but not limited to, ongoing or active infection, symptomatic congestive heart failure, unstable angina pectoris, cardiac arrhythmia, or psychiatric illness/social situations that would limit compliance with study requirements.
7. Subject has negative PSA doubling time (negative doubling time corresponds with decreasing PSA) Doubling time may be computed using the Sloan Kettering prediction tools posted at <http://www.mskcc.org/applications/nomograms/prostate/PsaDoublingTime.aspx>

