### 11.1 Analysis Plans for Primary Objective

**PSA Slope:** Eligible patients must have a rising PSA with a minimum of 3 time points but up to 17 time points (2 rises at least 21 days apart) within the 12 months prior to study initiation (this could include the PSA measurement taken at the screening visit, but not at the baseline day 0 study visit). The pre-treatment slopes will be calculated based on these data prior to baseline (day 0). A minimum of three time points but up to five time points will be used for calculating on-study slopes: baseline, 12, 24, 36, and 48 week assessments. All data points will be used unless an assessment is unavailable, in which case the remaining time points will be used. There must be a minimum of three data points, and there will be no imputation of missing PSA values.

The primary objective will be based on the intent-to-treat (ITT) population and assessed with an ANCOVA model, with post-treatment PSA slope as the independent variable and study arm and baseline PSA slope as covariates. A two-sided t test at the 0.05 significance level will be used to determine if, adjusting for baseline, the post-treatment PSA slope has been reduced with MPX supplementation (Arm A). Scatterplots of post treatment PSA slope by baseline slope will be used to visualize the fitted ANCOVA model. Boxplots of the observed changes will also be used to visualize the results.

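### Within-arm tests of on-study against baseline PSADT can show lengthening without any treatment effect, because the PSAs that define the baseline also had to be rising for entry

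*Combined protocol and SAP*

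**What the plan says.** Section 11.2 (PSA Doubling Time) lists two between-arm analyses of the log ratio of on-study to pre-treatment PSADT: a Wilcoxon rank-sum test and an ANOVA adjusted for the stratification factors. It then adds 95% confidence intervals for the change from baseline in each group, and a paired t-test or signed-rank test that "will be used to assess the within treatment group differences of PSADT on study compared to the baseline". A slope at or below zero is given a PSADT of 100 months.

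Entry (Section 3.1, criteria 3 and 4):
- "Subject has a rising PSA on a minimum of 3 time points (2 rises) within the 12 months prior to study initiation"
- "The three time points must be at least 21 days apart"
- "PSADT must be positive according to Memorial Sloan Kettering Cancer Center Prostate Cancer Nomograms"

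Criterion 3 allows fluctuations. Criterion 4 asks for an overall rising trend and for every available PSA from the last 12 months to be recorded. Section 3.2, criterion 7, excludes a negative PSADT.

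Section 11.1 ties the baseline to those same values: "The pre-treatment slopes will be calculated based on these data prior to baseline (day 0"). It foresees 3 to 17 of them. For the on-study period, "A minimum of three time points but up to five time points will be used for calculating on-study slopes", with no condition on their direction.

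**The concern.** A within-arm test of change is valid only if, without treatment, the expected change is zero. Here it is not. The baseline slope is a noisy measurement that also decided entry: men whose measured slope was falling, by chance or in truth, are screened out, and men whose measured slope was by chance too steep stay in. The on-study slope is a fresh measurement without that filter, so on average it moves back toward slower growth. The 100-month score adds to this, since the entry rules leave almost only on-study values able to receive it.

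What is at stake is interpretation. A significant lengthening within the MPX arm could be reported even if MPX does nothing, and a pattern of significance on MPX but not on placebo could arise by chance. Section 2.2.3 already presents before-and-after PSADT figures as part of the trial's rationale, so such a result may well be read as evidence of effect.

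**Working it through.** **1. Check of the slope model.** The plan gives no figure for the within-arm tests, so I first reproduced its power statement. Inputs from Section 11: 39 per arm, difference 0.05, SD 0.075, two-sided 5%. The standard error is 0.075 × √(2/39) = 0.0170 and the noncentrality is 0.05/0.0170 = 2.94. A noncentral t on 75 df gives 82.8% at ρ = 0 and, with SD × √(1−ρ²), 83.2% at ρ = 0.1 and 86.1% at ρ = 0.3. The plan states 83% and 87%, so the inputs are read correctly.

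**2. Shift in mean slope with no treatment effect.** Take pre and post slopes as bivariate normal with common mean μ and SD σ = 0.075. The plan gives this SD for the post-treatment slope; using the same mean and SD before treatment is my assumption. Keep only men with a positive pre-treatment slope. With λ = φ(μ/σ)/Φ(μ/σ), the mean pre slope among those enrolled is μ + σλ and the mean post slope is μ + ρσλ.

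| μ (per month) | λ | Mean pre slope | Mean post slope, ρ = 0.1 to 0.3 |
|---|---|---|---|
| 0.0462 (PSADT 15 months) | 0.4514 | 0.0801 | 0.0496 to 0.0564 |
| 0.083 (the plan's control value) | 0.2498 | 0.1017 | 0.0849 to 0.0886 |
| 0.1155 (PSADT 6 months) | 0.1299 | 0.1252 | 0.1165 to 0.1184 |

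For example, at 0.083: 0.083 + 0.075 × 0.2498 = 0.1017 before, and 0.083 + 0.1 × 0.075 × 0.2498 = 0.0849 after.

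**3. Effect on PSADT and the signed-rank test.** Same model, simulated for one arm of 39 men, PSADT = ln 2/slope, 100 months if slope ≤ 0. Test level taken as two-sided 5% (Section 11.2 states none), so the nominal rate for lengthening is 2.5%. Rates are rounded over repeated independent runs.

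| μ | Median PSADT, baseline → on-study (ρ = 0.1 to 0.3) | Geometric mean ratio | False lengthening |
|---|---|---|---|
| 0.0462 | 9.7 → 13.9 to 12.3 months | 1.67 to 1.50 | roughly 40-60% |
| 0.083 | 7.2 → 8.2 to 7.8 months | 1.34 to 1.28 | 16-23% |
| 0.1155 | 5.7 → 6.0 to 5.8 months | 1.16 to 1.13 | 7-8% |

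Between 6% and 25% of on-study slopes are at or below zero and become 100 months.

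**4. Dependence on the entry PSAs.** PSA-level simulation: 39 men, mean slope 0.083, between-man SD 0.05, slopes unchanged by treatment, five on-study PSAs. PSA noise is not in the documents; 10-20% is assumed. The shortest permitted span is 2 × 21 = 42 days, or six weeks. Signed-rank false lengthening:

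| Entry PSAs | Both steps must rise | Positive slope only |
|---|---|---|
| 3 over 6 weeks | 98-100% | 26-86% |
| 3 over 3 months | 44-99% | about 4-34% |
| 3 over 6 months | 8-51% | 2-6% |
| 3 over 11 months | 4-13% | 1-6% |

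With five PSAs over 11 months the rate is about 2-8%.

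**5. Paired t-test.** In most PSA-level scenarios its rate is lower (both steps rising: 15-72% at 3 months, 2-22% at 6 months). Under the slope model of steps 2 and 3 it is higher than the signed-rank rate. On raw months it is also unstable: a positive baseline slope of 0.004, for instance, gives 0.693/0.004 = 173 months, uncapped, while a falling on-study PSA scores 100.

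**The case against.** The strongest reply is about scope. No within-arm p-value is a success criterion. The primary test is a between-arm ANCOVA, Section 11.2 names the between-arm PSADT tests first, the secondary objective is only to estimate PSADT in the two groups, and Section 11.4 labels everything else secondary or exploratory. All of that stands and keeps the point to reporting. The label answers multiplicity, however; it does not repair a test whose null hypothesis is already wrong before any capsule is taken.

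The second reply is about size, and much of it stands. A reader might infer from the minimum entry rule that false lengthening is nearly certain, or that every baseline is a strict run of rises. The documents support neither. The near-100% figure needs every man to have exactly three PSAs, both steps rising, within six weeks; that is permitted, not shown to be typical. Fluctuations are allowed, all PSAs of the past year are to be recorded, and up to 17 may be used. With fuller histories the rate approaches nominal.

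A reader might also infer that the cited placebo data prove the effect. They are consistent with it and no more. The phase II placebo change is reported as "with a change of 0.9 months seen in the placebo group", without a stated direction. The 1.8-month median among AA controls rests on four men. The pomegranate placebo change (10.9 to 12.7 months) comes without an interval.

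**Conclusion.** The point holds as one about the within-arm tests and the per-arm confidence intervals for change in PSADT. Their reference value of no change is not what an ineffective treatment would be expected to give, so apparent lengthening can occur in both arms.

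The direction follows from the entry rules and the plan's own slope model. The size is uncertain: it rests on equal pre-treatment mean and SD in the slope model, and on assumed PSA noise and entry histories in the PSA-level simulation. Across those assumptions the false signed-rank rate runs from near nominal to near 100%.

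It would be wrong to extend this to the primary ANCOVA or to the between-arm PSADT tests. Randomisation applies the same entry selection to both arms, so those comparisons are not biased by it.

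**What to change.** In Section 11.2:

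1. Delete the within-arm paired t-test and signed-rank test, or label them and the per-arm confidence intervals for change as descriptive only, not evidence of effect.
2. Report the between-arm difference in log(on-study PSADT/baseline PSADT) with its 95% confidence interval, from the stratification-adjusted ANOVA already planned.
3. Add one sentence stating that PSADT may lengthen in both arms without treatment effect because entry requires a rising PSA.

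The cost is a wording change and, at most, the loss of one supplementary test. No data collection, sample size or primary analysis is affected.
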